3.1 PRIMARY ENDPOINT

- *Efficacy primary endpoint*
 - 1-month[†] all-cause mortality rate. [†](Day 30 since randomisation).

3.2 KEY SECONDARY ENDPOINT.

- Time to confirmed negativisation in SARS-CoV-2 antigen test or RT-PCR Ct > 30.

3.3 SECONDARY ENDPOINTS

3.3.1 Efficacy secondary endpoint

- Time to sustained end of COVID-related hospital care from the time of randomisation. Sustained discharge is defined as no subsequent admission within 30 days of initial end of hospital care [up to day 60 (±3)], related to either COVID-19 or COVID-19 therapy.
- Time to sustained improvement (defined in [Section 7.1.3](#)) and resolution of selected COVID signs/symptoms (See [Appendix 10 - COVID-19 signs/symptoms checklist](#)).
- Distribution of patients according to their clinical status by the 11-category WHO Clinical Progression Scale, at Days 4 (±1), 8 (±1), 15 (±1), 30 (±2), and 60 (±3) (See [Appendix 1 – 11-Point World Health Organization \(WHO\) Clinical Progression Scale](#)).
- Percentage of patients requiring oxygen therapy on Days 4 (±1), 8 (±1), 15 (±1), 30 (±2), and 60 (±3).
- Time to sustained discontinuation (i.e., at least 7 days) of oxygen supplementation.

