7.1.4 Other Efficacy Assessments

The study day (from Day 1 to Day 60 (± 3 days)) on which the following events occurred will be recorded:

- Initiation of supplemental oxygen (of any type)
- Discontinuation of supplemental oxygen (of any type)
- Initiation of respiratory support
- Discontinuation of respiratory support
- Initiation of antivirals or immune-modulating drugs
- Discontinuation of antivirals or immune-modulating drugs
- ICU admission
- ICU discharge
- Subsequent hospital admission for COVID-19 signs or symptoms
- Hospital discharge
- Death

Additionally, the following information will be gathered for each patient on Days 4, 8 (± 1 day), 15 (± 1 day), and 30 (± 2 days) (yes/no):

- Receiving supplementary oxygen therapy
- Receiving high-flow oxygen
- Receiving non-invasive mechanical ventilation
- Receiving invasive mechanical ventilation or ECMO
- Requiring hospital admission related to COVID-19
- Requiring ICU admission
- Receiving subsequent antiviral therapies or immunomodulatory
- Occurrence of new infection
- Death

Based on these data, secondary endpoints for percentages of patients requiring oxygen therapy or different types of ventilation will be calculated and the time (in days) to sustained hospital discharge or withdrawal of supplemental oxygen therapy, percentages of patients with new infection or receiving subsequent antiviral or immunomodulatory therapies, hospitalisation in ICU, and hospitalisation will be measured.

Laboratory based efficacy assessments that are to be performed during the study include:

- Proinflammatory biomarkers: (CRP, LDH, ferritin, cytokine multiplex Luminex[®] panel, including IL-1 β , IL-6, IL-10, and TNF α) in each study arm from baseline (Day 1 prior to start of the study treatment) to on Days 4 (± 1 day), 8 (± 1 day), 15 (± 1 day), 30 (± 2 days), and 60 (± 3 days),
- Anti-SARS-CoV-2 serologic and cellular response will be centrally assessed by validated tests, on Days 1, 30 (± 2 days), and 60 (± 3 days).

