8.6.2.1 Full Analysis Set (FAS) Population

All randomised patients who have taken at least 1 dose of study treatment (plitidepsin or control) and have completed follow-up for survival until day 30 (± 2). Patients who die before the end of follow-up period will also be included in the FAS population. FAS population will be analysed according to their randomised treatment arm.

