9.0 Conventions and Derivations

Variables reported with different units will be homogenized to standardized variables following the International System of Units (e.g. laboratory tests, biometrical assessments...) unless otherwise specified.

By default, all results will be rounded to one decimal place, except when variables are integer, which will be reported without decimals (e.g., age in years). Percentages for 0 counts will not be presented and 100% values will be presented with no decimal places. For representing p-values four decimals will be selected as default but they could be rounded to fewer decimals if necessary.

Missing values will not be included in the calculation of outputs. Unless otherwise noted, missing data will not be imputed or carried forward.

For patients who discontinue treatment due to adverse events (related or not to study treatment) every effort should be made to remain under study follow-up, anyway, if information is lost before day 28 the conservative value of death will be also imputed.

Patients with no available data for any time-to event efficacy endpoint will be censored at time 0. EOS: Day 60 (± 3) or date of early study termination, if applicable. Patients not yet achieving the time to event endpoint will be censored at the last valid assessment prior to EOS. Efron's method will be used to handle ties.

Assessment windows as specified in the clinical protocol will be respected, see protocol Appendix 13 'Schedule of Assessments and Procedures' for definitions of trial days. Baseline is defined as latest test performed between screening and drug administration.

Change from baseline (%) is defined as: $(\text{test value} - \text{baseline value}) / \text{baseline value} \times 100$.

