11.8 Summary of Statistical Tests

All the main characteristics for estimands to fulfill study objectives will be defined as footnotes in each table following a similar structure than primary estimand definition. Below it can be found the endpoints to measure the variable definition and the analysis method to be used. Treatment attribute is maintained as 'participants will be randomised to receive plitidepsin versus control in each group' whereas applicable and sensitivity analyses according populations defined in 8.5 will be calculated. For intercurrent events, while applicable, a treatment-policy strategy as defined for the primary estimand will be followed.

Table 3 Summary of statistical tests

Endpoints	Analyses	Population
Efficacy primary endpoint		
1-month all-cause mortality rate.	-Frequencies	-FAS population
Key secondary endpoint		
Time to confirmed negativisation in SARS-CoV-2 antigen test or RT-PCR Ct > 30.	-Kaplan-Meier (unstratified)	-FAS population

Endpoints	Analyses	Population
Efficacy secondary endpoints		
Time to sustained end of COVID-related hospital care from the time of randomisation. Sustained discharge is defined as no subsequent admission within 30 days of initial end of hospital care [up to day 60 (± 3)], related to either COVID-19 or COVID-19 therapy	-Kaplan-Meier (unstratified)	-FAS population
Time to sustained improvement (defined in Protocol Section 7.1.3) and resolution of selected COVID signs/symptoms (See Protocol Appendix 10 - COVID-19 signs/symptoms checklist).	-Kaplan-Meier (unstratified)	-FAS population
Distribution of patients according to their clinical status by the 11-category WHO Clinical Progression Scale, at Days 4 (± 1), 8 (± 1), 15 (± 1), 30 (± 2), and 60 (± 3) (See Protocol Appendix 1 – 11-Point World Health Organization (WHO) Clinical Progression Scale).	-Frequencies	-FAS population
Percentage of patients requiring oxygen therapy on Days 4 (± 1), 8 (± 1), 15 (± 1), 30 (± 2), and 60 (± 3).	-Frequencies	-FAS population
Time to sustained discontinuation (i.e., at least 7 days) of oxygen supplementation.	-Kaplan-Meier (unstratified)	-FAS population
Safety secondary endpoints		
Treatment-emergent adverse events (TEAEs).	-Frequencies (severity grade by NCI-CTCAE v5)	-As treated population
TEAEs \geq grade 3 according to the National Cancer Institute	-Frequencies	-As treated population

Endpoints	Analyses	Population
[NCI]-Common Terminology Criteria for AEs (CTCAE v.5.0).		

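### Sustained discharge carries no survival condition, and neither the protocol nor the SAP says how a death before or after discharge enters the endpoint

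*Protocol*

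**What the plan says.** Protocol 3.3.1 lists time from randomisation to sustained end of COVID-related hospital care. It qualifies the term as follows: "Sustained discharge is defined as no subsequent admission within 30 days of initial end of hospital care", with a limit at Day 60 (±3) and counting only admissions "related to either COVID-19 or COVID-19 therapy". The synopsis, the analysis table in Protocol 8.5, SAP 8.3 and SAP 11.8 repeat the definition. The protocol planned unstratified Kaplan-Meier and Cox analyses. SAP version 3.0, abridged after early closure, keeps the unstratified Kaplan-Meier analysis in the FAS.

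Four other rules bear on deaths:

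- **Analysis set (SAP 8.6.2.1):** "Patients who die before the end of follow-up period will also be included in the FAS population".
- **Censoring (SAP 9.0):** "Patients not yet achieving the time to event endpoint will be censored at the last valid assessment prior to EOS".
- **Imputation (SAP 9.0), for patients who stop treatment because of adverse events:** "if information is lost before day 28 the conservative value of death will be also imputed".
- **Intercurrent events (SAP 11.8):** "For intercurrent events, while applicable, a treatment-policy strategy as defined for the primary estimand will be followed". The primary estimand in SAP 11.6.1 names two such events, treatment discontinuation and the start of non-protocol therapy.

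Protocol 7.1.4 has sites record the study day of hospital discharge, of death, and of "Subsequent hospital admission for COVID-19 signs or symptoms".

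**The concern.** The endpoint is meant to show that the patient left hospital care and did well enough not to return. A patient who dies at home cannot be readmitted, so death itself satisfies a condition that asks only for the absence of readmission. In a population for which the sample-size example assumes 20% control mortality, this is a realistic outcome.

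Death before discharge raises the opposite problem. Kaplan-Meier censoring assumes that the censored patient could still have the event later, at the same rate as those still under observation. A patient who has died in hospital cannot.

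At stake is whether the discharge curve can be read as recovery, and whether two programmers working from the same SAP would draw the same curve. SAP section 6.0 says the descriptive tables will allow numerical comparison of the arms, so the curve will be read that way even without a test.

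**Working it through.** The plan gives no target rate, power or event count for this endpoint, so there is no figure to reproduce. The check sets the rules against three cases and then illustrates their scale.

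**Case A: death after discharge.** A patient is discharged on Day 10, dies at home on Day 20 and is never readmitted.

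1. The readmission window runs from Day 10 to Day 10 + 30 = Day 40, inside the Day 60 limit.
2. There is no COVID-related admission in that window, so the written condition is met. The natural event date is the initial end of hospital care, Day 10.
3. The FAS rule keeps the patient in the analysis.
4. The censoring rule covers only patients who have not achieved the endpoint. On the literal definition, this patient has.
5. The imputation rule concerns information lost before Day 28, not a known death.
6. The intercurrent-event strategy carried over from the primary estimand does not list death.

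No rule reverses step 2.

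**Case B: a later death after discharge.** A patient is discharged on Day 25 and dies at home on Day 40 without readmission. The window runs to Day 25 + 30 = Day 55. The patient is alive for the primary endpoint at Day 30 and also meets the sustained-discharge definition. The death appears only in the Day 60 mortality and safety tables.

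**Case C: death before discharge.** The patient has not achieved the endpoint, so SAP 9.0 censors at the last valid assessment.

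**Scale of A and B (illustration).** Inputs: n = 20 per arm (Protocol 8.1) and an assumed 16 patients discharged without COVID-related readmission, of whom d die in the window. With no other censoring before Day 60:

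- As written: 16/20 = 80%, whatever d is.
- With survival required: (16 − d)/20, which is 75%, 70% and 65% for d = 1, 2 and 3.
- Shift per death: 1/n = 1/20 = 5 points. It is larger for any n below 20.

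**Scale of C (illustration).** Protocol 8.1 uses 20% control mortality in its example, and 0.20 × 20 = 4 deaths. Assume all four occur in hospital and the other 16 patients reach sustained discharge.

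- Deaths kept in the risk set as non-events: the curve ends at 16/20 = 80%.
- Deaths censored before the first discharge: after k discharges the curve reads k/16 instead of k/20, and it ends at 16/16 = 100%.
- Deaths censored after the last discharge: the curve ends at 80%.

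The final level can therefore lie anywhere from 80% to 100%, depending only on when the deaths fall among the discharges.

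**The case against.** The strongest reply is that the documents are silent on such deaths. They nowhere call them successes. A patient who dies on Day 20 after discharge on Day 10 has not been observed for a full 30 days without readmission. A programmer could treat that patient as not yet having achieved the endpoint and censor under SAP 9.0. SAP 11.8 also defers estimand details to table footnotes, which are not among the documents. This stands in part: a reader might infer that the plan deliberately scores death as recovery, and the text does not support that. But no text instructs censoring either, and censoring would treat a dead patient as still able to reach sustained discharge. Both readings need a written rule.

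Second, the endpoint is cause-specific by design, since an unrelated readmission does not defeat it; requiring survival from any cause changes that concept. This is a fair point about choice of estimand. It does not rescue the wording, because a death at home from COVID-19 itself also meets the definition.

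Third, the consequence is limited, and this stands. The endpoint is a non-key secondary one, and version 3.0 of the SAP presents no formal tests. All-cause deaths are reported at Day 30 as the primary endpoint, cumulatively to Day 60, and as a safety endpoint.

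Fourth, no size can be asserted. The documents give no count of deaths after discharge, and 20 per arm is a plan that early closure has overtaken. Deaths that follow a COVID-related readmission already fail the definition. Similar numbers of such deaths in both arms would largely cancel in a comparison. All of this stands.

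**Conclusion.** The point holds as a defect in the endpoint definition and its censoring rule. As written, survival is not needed for sustained discharge, nothing elsewhere in the protocol or SAP adds it, and deaths before discharge are censored as if discharge were still possible.

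A reader might go further and infer that the sustained-discharge rate is overstated by a particular number of points, or that the comparison of arms is biased in one direction. The documents support neither: they give no number of such deaths and nothing on how they would divide between arms. What can be said is 1/n per death after discharge without COVID-related readmission, which is 5 points at the planned 20 and more in smaller arms. The 80% to 100% range for in-hospital deaths rests on four assumed deaths in an arm of 20.

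The effect is confined to interpreting one descriptive secondary endpoint. It does not touch the primary mortality result. The conclusion rests on the literal wording; the protocol appendices and table shells were not available, and the definition refers to none of the appendices.

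**What to change.** Define the event as end of hospital care with the patient alive and not readmitted for COVID-19 or its therapy through 30 days after that date or Day 60, whichever is first. Treat any death before that point, whether before or after discharge, as a non-event kept in the risk set to Day 60. Equivalently, treat death as a competing event and report the cumulative incidence of sustained discharge. Covering both kinds of death matters: a rule for post-discharge deaths alone would leave in-hospital deaths censored and the endpoint internally inconsistent.

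State the definition in SAP 8.3 and 11.8 and the death rule in SAP 9.0, as an exception to the general censoring sentence, or put both in the table footnotes that SAP 11.8 already promises. With recruitment ended, a protocol amendment would add little. Any later protocol using this endpoint should carry the corrected wording.

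The cost is a few sentences and a small change to the derivation program. No new data are needed, since the study days of discharge, later admission and death are already recorded. Showing the number of deaths before and after discharge beneath the curve, by arm, would let the reader judge how much the rule matters.

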3.3.2 Safety secondary endpoints

Frequency of the following events (all-cause and drug-related):

- Treatment-emergent adverse events (TEAEs);
- TEAEs ≥ grade 3 according to the National Cancer Institute [NCI]-Common Terminology Criteria for AEs (CTCAE v.5.0);
- Adverse events of special interest (AESIs);
- Serious adverse events (SAEs);
- Drug related Serious Adverse Events (i.e., SARS);
- Adverse events leading to treatment discontinuation; and
- Deaths (COVID-19-related/all).
- Change respect to baseline* in individual study-defined laboratory parameters (See [Section 5.7, 5.8](#) and [5.9](#) and [Appendix 8 - Clinical Laboratory Analyses](#)).
- Change respect to baseline* in individual vital signs (See [Section 5.7, 5.8](#) and [5.9](#)).

*Baseline = latest test performed between screening and drug administration

3.3.3 Other secondary/exploratory endpoints

- Percentage of patients requiring advanced oxygen support on Days 4 (± 1), 8 (± 1), 15 (± 1), 30 (± 2), and 60 (± 3).
- Time to intensification of respiratory support (WHO >5) (See [Appendix 1 – 11-Point World Health Organization \(WHO\) Clinical Progression Scale](#)).
- Total duration of advanced oxygen support.
- Percentage of patients requiring high-flow oxygen on Days 4 (± 1), 8 (± 1), 15 (± 1), 30 (± 2), and 60 (± 3).
- Total duration of high-flow oxygen therapy per patient.
- Percentage of patients requiring non-invasive mechanical ventilation on Days 4 (± 1), 8 (± 1), 15 (± 1), 30 (± 2), and 60 (± 3).
- Total duration of non-invasive mechanical ventilation per patient.
- Percentage of patients requiring invasive mechanical ventilation or ECMO on Days 4 (± 1), 8 (± 1), 15 (± 1), 30 (± 2), and 60 (± 3).
- Total duration of invasive mechanical ventilation or ECMO per patient
- Percentage of patients requiring admission to ICU on Days 4 (± 1), 8 (± 1), 15 (± 1), 30 (± 2), and 60 (± 3).
- Total duration of intensive care unit (ICU) stay.
- Time to onset of additional (i.e., not present at baseline) immune-modulating drugs.
- Percentage of patients receiving immune-modulating drugs on Days 1, 4 (± 1), 8 (± 1), 15 (± 1), 30 (± 2), and 60 (± 3).
- Time to onset of additional (i.e., not present at baseline) antiviral drugs.
- Percentage of patients receiving subsequent antiviral drugs (i.e., not present at baseline) on Days 4 (± 1), 8 (± 1), 15 (± 1), 30 (± 2), and 60 (± 3).
- Percentage of patients with a new infection by Days 4 (± 1), 8 (± 1), 15 (± 1), 30 (± 2), and 60 (± 3).
- Cumulative mortality (all-cause and related to COVID-19) by Days 4 (± 1), 8 (± 1), 15 (± 1), 30 (± 2), and 60 (± 3).
- Percentage of patients in each study group who require subsequent admission within 30 days of initial end of hospital care [up to Day 60(± 3)], related to either COVID-19 or COVID-19 therapy.
- Change respect to Day 1 in the viral load of SARS-CoV-2, measured by RT-PCR, by Days 4 (± 1), 8 (± 1), 15 (± 1), 30 (± 2), 45 (± 2), and 60 (± 3), in each study group.
- Percentage of patients in each study group with undetectable viral load, by Days 4 (± 1), 8 (± 1), 15 (± 1), 30 (± 2), 45 (± 2), and 60 (± 3).
- Time to either undetectable viral load of SARS-CoV-2 or > 2 logs reduction respect to Day 1
- Change respect to baseline* in inflammatory and immunological (C- reactive protein [CRP], procalcitonin, lactate dehydrogenase [LDH], ferritin, neutrophil-to-

lymphocyte ratio, ALC, D-dimer, and multiplex cytokines assay, by Day 4 (± 1), 8 (± 1), 15 (± 1) and 30 (± 2) and 60 (± 3).

- Change respect to baseline* in individual serological assessments against SARS-CoV-2, by Days 30 (± 2), and 60 (± 3).
- Change respect to baseline* in individual T-cell response against SARS-CoV-2 by Days 30 (± 2), and 60 (± 3).
- Change respect to baseline* to Days 15 (± 1), and 30 (± 2) in chest X-ray findings (Brixia score, centrally assessed) ([Appendix 9 – Brixia Score](#)).
- Percentage of patients requiring modification of the therapy (drugs, dose or schedule) for the underlying disease.
- Time in which pre-scheduled therapies for the control of the underlying disease were not able to be administered.
- Risk for mortality / clinical deterioration according to individual clinical characteristics and laboratory observations present at baseline*, scores of validated scales (e.g., ISARIC-4C), as well as features related to COVID-19 [including SARS-CoV-2 variant (if available), vaccination status, duration of the infection, and inflammation-related parameters [neutrophil-to-lymphocyte ratio (NLR), protein C reactive, interleukine-6 (IL-6) and lymphocytes], the underlying disease, and other co-morbidities.
- Limited-sampling pharmacokinetics assessment (See [Section 7.6](#)).
- PK-PD analysis.

*Baseline = latest test performed between screening and drug administration

